#### **Sample Size Justification:**

The proposed sample size is based on feasibility and availability of resources. The proposed enrollment period for this study will be one year, and it is estimated that approximately 140 subjects meeting the qualification criteria will be seen during the enrollment period at the participating sites. It is expected that nearly all of these patients will consent to participate. Due to the screen failure rate of approximately 30% till date we want to enroll a total of 140 subjects to account for the screen failures.

Total Number of Subjects in Study	Number of Subjects with stone seen on POC	Percent of Subjects with stone seen on POC	95% Exact Binomial Confidence Interval
100	10	10.0%	4.9% - 17.6%
	20	20.0%	12.7% - 29.2%
	30	30.0%	21.2% - 40.0%

Based on literature cited earlier, it is estimated that between 11% and 30% of these patients will have stones identified on POC that were missed by conventional ECRP. The following table gives the 95% exact binomial confidence intervals for the proposed sample size of 100 subjects, if the percent with missed stones is 10%, 20% and 30%. (For example, if 20 subjects have missed stones, the estimated percent with missed stones is 20% and the associated 95% exact binomial confidence interval is 12.7% to 29.2%).

### 13. SPECIMEN BANKING

- *If specimens will be banked for future research, describe where the specimens will be stored, how long they will be stored, how they will be accessed and who will have access to the specimens*
- *List the information that will be stored with each specimen, including how specimens are labeled/coded*
- *Describe the procedures to release the specimens, including: the process to request release, approvals required for release, who can obtain the specimens, and the information to be provided with the specimens.*

N/A
-----

### 14. DATA MANAGEMENT AND CONFIDENTIALITY

- *Describe the data and specimens to be sent out or received. As applicable, describe:*
  - *What information will be included in that data or associated with the specimens?*
  - *Where and how data and specimens will be stored?*
  - *How long the data will be stored?*
  - *Who will have access to the data?*
  - *Who is responsible for receipt or transmission of data and specimens?*
- *Describe the steps that will be taken to secure the data during storage, use and transmission.*

The principal investigator will be responsible for the management of the protocol. All efforts will be made to ensure patient confidentiality and assurance of HIPAA compliance. Immediately after obtaining any images, subjects will be assigned a protocol specific unique code that will be used for all further data management. A list matching the patient medical record number to the protocol specific unique code will be kept in a locked cabinet in office of the PI. The names of the patient will not be released to any outside organizations or to persons not involved with the study. They will not be revealed in written reports or publications detailing the research findings. However the information may be released to regulatory authorities such as IRB, FDA etc.

---

### 15. DATA AND SAFETY MONITORING PLAN

*A specific data and safety monitoring plan is only required for greater than minimal risk research. For guidance on creating this plan, please see the [Guidance Document](#) on the HRPP website.*

*Part I – this part should be completed for all studies that require a DSMP.*

*Part II – This part should be completed when your study needs a Data and Safety Monitoring Board or Committee (DSMB/C) as part of your Data and Safety Monitoring Plan.*

## Part I: Elements of the Data and Safety Monitoring Plan

- *Indicate who will perform the data and safety monitoring for this study.*
- *Justify your choice of monitor, in terms of assessed risk to the research subject's health and well being. In studies where the monitor is independent of the study staff, indicate the individual's credentials, relationship to the PI, and rationale for selection*
- *List the specific items that will be monitored for safety (e.g. adverse events, protocol compliance, etc)*
- *Indicate the frequency at which accumulated safety and data information (items listed in # above) will be reviewed by the monitor (s) or the DSMB/C.*
- *Where applicable, describe rules which will guide interruption or alteration of the study design.*
- *Where applicable, indicate dose selection procedures that will be used to minimize toxicity.*
- *Should a temporary or permanent suspension of your study occur, in addition to the IRB, indicate to whom will you report the occurrence.*

N/A

## Part II: Data and Safety Monitoring Board or Committee

- *When appropriate, attach a description of the DSMB.*
- *Provide the number of members and area of professional expertise.*
- *Provide confirmation that the members of the board are all independent of the study.*

N/A

## 16. WITHDRAWAL OF SUBJECTS

- *Describe anticipated circumstances under which subjects will be withdrawn from the research without their consent*
- *Describe procedures for orderly termination*
- *Describe procedures that will be followed when subjects withdraw from the research, including partial withdrawal from procedures with continued data collection.*

Consented patients will be withdrawn from participation and their data will not be used if the standard of care procedures described in the protocol cannot be performed for any clinical reason such as inaccessibility of bile duct, early termination of procedure due to complications etc. The 3 month follow-up phone call will not be made if the standards of care procedures are not completed and data not collected.

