## 8. NUMBER OF SUBJECTS

- *Indicate the total number of subjects to be accrued locally. If applicable, distinguish between the number of subjects who are expected to be pre-screened, enrolled (consent obtained), randomized and complete the research procedures.*
- *If your study includes different cohorts, include the total number of subjects in each cohort.*
- *If this is multisite study, include total number of subjects across all sites.*

Number of patients: 100 who undergo POC in NSUH and in LIJMC

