**Clinically indicated standard of care procedure/s:**

ERCP will be performed with cannulation of the bile duct and cholangiogram to identify any biliary stones. If stones are identified, they will be removed with conventional methods including sphincterotomy, sphincteroplasty, balloon extraction, basket retrieval, and/or lithotripsy. An occlusion cholangiogram will be performed to confirm duct clearance (usually performed by inflating the catheter balloon at the proximal common hepatic duct near the hilum and then pulling the balloon through the bile duct and into the duodenum. Then, based on clinical decision and inclusion criteria, the cholangioscope (Spyglass) will be inserted through the channel of the endoscope and into the bile duct. Any residual stones will be documented followed by further treatment as indicated e.g. stone extraction, lithotripsy, stent placement, etc.

All patients with suspected cholechodoliathiasis potentially meeting the Inclusion criteria will be enrolled in the study. This is the reason for taking the consent before hand when the patient is not sedated. However if on clinical judgment during the procedure, the physician decides not to perform the POC then the subject will be deemed as screen failure and will not be counted towards the final results of the study.

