#### **Endpoint Variables:**

1. Missed stones: Patients will be considered to have missed stones on conventional ERCP, if, after ERCP, one or more stones are seen with POC.
2. Change in management: any maneuver or combination of maneuvers performed after a missed stone (e.g. balloon extraction of stone, lithotripsy of stone, stent placement, etc.)
3. Recurrent stones within 3 months after POC, and documentation of cholecystectomy as applicable.

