#### **Statistical Methods:**

1. The proportion of subjects with missed stones will be estimated, along with the associated exact 95% binomial confidence interval.
2. Change in management will be described by calculating frequencies and percentages for each maneuver performed. This analysis will be restricted to subjects with missed stones.
3. The proportion of subjects with recurrent stones will be estimated, along with the associated exact 95% binomial confidence interval.

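### Section 16, read literally, can discard a missed stone already seen on cholangioscopy if the procedure is then stopped early; it conflicts with Sections 8 and 11, and the net effect on the missed-stone rate is not established

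*Combined protocol and SAP*

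**What the plan says.** Section 16 (Withdrawal of Subjects) withdraws consented patients and states that "their data will not be used if the standard of care procedures described in the protocol cannot be performed for any clinical reason". It gives two examples: a bile duct that cannot be reached, and "early termination of procedure due to complications etc". It then adds: "The 3 month follow-up phone call will not be made if the standards of care procedures are not completed and data not collected".

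The procedures meant are those in Section 11 under the clinically indicated standard-of-care heading. They run in order: ERCP with stone removal, occlusion cholangiogram, cholangioscope, and finally "Any residual stones will be documented followed by further treatment as indicated e.g. stone extraction, lithotripsy, stent placement, etc". Treatment after POC therefore stands under the same heading as the POC itself.

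Section 12 (Endpoint Variables) defines the primary outcome: "Patients will be considered to have missed stones on conventional ERCP, if, after ERCP, one or more stones are seen with POC". The analysis is one proportion: "The proportion of subjects with missed stones will be estimated, along with the associated exact 95% binomial confidence interval". Section 12 defines no analysis set.

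Three other places bear on who is counted:

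- Section 8 sets the target as "Number of patients: 100 who undergo POC in NSUH and in LIJMC".
- Section 11, research procedures item 4, plans the contact at about 3 months for enrolled patients who had cholangioscopy. It does not require later treatment to be complete.
- Section 17 has procedural risks that arise recorded on the CRF for use in the analysis.

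**The concern.** The primary endpoint is settled when a stone is seen. Nothing done afterwards can change it. Section 16 nevertheless lets a later event, such as a complication during treatment of that stone, decide whether the patient is analysed. An inclusion rule that acts after the outcome is known, and through steps that only one outcome group goes through, can bias a proportion. The exact binomial interval covers sampling error only and would not show this.

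The same discard would take the patient out of the change-in-management table, which is restricted to subjects with missed stones. It could also cast doubt on whether that patient receives the 3-month call. Two people working from different sections could count the same patient differently: Sections 8 and 11 keep the patient, and Section 16 does not.

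**Working it through.** **1. The plan's own figures.** For 10, 20 and 30 positives out of 100, the exact (Clopper-Pearson) 95% intervals are 4.9% to 17.6%, 12.7% to 29.2% and 21.2% to 40.0%. They match the table in Section 12 to the decimal. The table takes all 100 patients as analysed.

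**2. When each rule acts.**

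| Stage at which the procedure stops | Is the POC result known? | Section 16 read literally | Sections 8 and 11 (item 4) |
|---|---|---|---|
| Before the cholangioscope is used | No | Discard | Not counted (no POC) |
| During POC, no stone yet seen | Not settled | Discard | POC begun; the text does not say whether this counts |
| After a stone is seen, during its treatment | Yes, positive | Discard | Counted and followed up |
| After a complete negative POC | Yes, negative | No described step left to fail | Counted and followed up |

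The third and fourth rows show the asymmetry. Once POC is complete, only stone-positive patients have a described step still ahead of them.

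**3. Effect of the third row alone.** Let k of n patients have a stone seen, and let r of those be discarded. The reported rate is (k − r)/(n − r), which is below k/n whenever r ≥ 1 and k < n. The documents give no rate of termination after POC, so r is assumed. The values of k are those in the Section 12 table, with n = 100.

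| k of 100 | r = 1 | r = 2 | r = 5 |
|---|---|---|---|
| 10 (10.0%) | 9/99 = 9.1% | 8/98 = 8.2% | 5/95 = 5.3% |
| 20 (20.0%) | 19/99 = 19.2% | 18/98 = 18.4% | 15/95 = 15.8% |
| 30 (30.0%) | 29/99 = 29.3% | 28/98 = 28.6% | 25/95 = 26.3% |

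One or two losses lower the estimate by 0.7 points (30/100, r = 1) to 1.8 points (10/100, r = 2). At 20/100 the interval moves from 12.7%–29.2% to 12.0%–28.3% (r = 1) or 11.3%–27.5% (r = 2).

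**4. Adding the second row.** Let s patients with an incomplete inspection and no stone seen also be discarded. The rate becomes (k − r)/(n − r − s). It is below k/n only if s < r(n − k)/k. For k = 20 and n = 100 that is s < 4r: four such discards cancel one lost positive. Assumed examples:

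- r = 1, s = 0: 19/99 = 19.2%
- r = 1, s = 4: 19/95 = 20.0%
- r = 1, s = 5: 19/94 = 20.2%
- r = 2, s = 8: 18/90 = 20.0%

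The comparison with 20/100 treats the s patients as having no stone seen; their true state is unknown. The documents give neither r nor s, so the sign of the net effect cannot be worked out.

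**The case against.** The strongest reply is that Section 16 was never meant for patients with a POC result. It speaks of procedures that cannot be performed, its first example comes before POC, and the sentence on the phone call adds the condition that data were not collected. Sections 8 and 11 tie counting and follow-up to having had POC, and Section 11 has stones documented before they are treated. This may well be the intent. However, the data-collected condition qualifies the call, not the sentence that bars the data, and early termination carries no time limit. If that was the intent, the fix only writes it down.

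A second reply is that a failed extraction need not trigger the rule. Section 11 lists later treatments as examples, to be used as indicated, and Section 12 accepts any maneuver or combination of maneuvers as a change in management. That stands. An extraction that fails and is followed by a stent is a recorded change in management. The point is confined to a procedure ended early after a stone was seen.

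A reader might also infer that the rule lowers the missed-stone rate overall, or that it strips out the hardest stones. The documents support neither. Stops during POC can remove non-events and offset the loss, as step 4 shows. The named triggers are access and complications, not stone difficulty.

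The screen-failure rule in Section 11 does not resolve the matter. It covers patients in whom the physician decides against POC, and they have no result to lose.

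**Conclusion.** The point holds as a conflict in the text with a possible effect on the primary estimate. Section 16 as worded can remove a confirmed primary event, and it disagrees with Sections 8 and 11 on whether that patient counts.

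Discards after a completed POC act downward when taken alone, by about 1 to 2 points for one or two losses. That is small against the planned interval, which at 20/100 reaches 7.3 points below the estimate and 9.2 above. It is not negligible when Section 12 expects a rate of 11% to 30%, so that only 11 to 30 events are likely among 100 patients. A larger sample would not remove it.

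The net direction and size are not established, because they depend on how many stops occur at each stage. All the loss counts used here are assumptions. The correction is still worth making before the data are analysed, because it settles who is in the primary analysis at almost no cost.

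**What to change.** - In Section 16, confine the bar on using data to patients in whom the cholangioscope never entered the bile duct.
- In Section 12, define the primary analysis set as all eligible, consented patients in whom it did enter. Count any stone seen as a missed stone, whatever happens afterwards, and keep these patients in the change-in-management table and the 3-month call.
- Record POC inspection on the CRF as complete or incomplete, and report the number and timing of early terminations.
- Give the primary proportion and its exact interval twice: once with incomplete no-stone inspections in the denominator, and once with them left out. Remove no observed stone from either. For example, with 20 stones among 100 patients entered and an assumed 5 incomplete no-stone inspections, the pair is 20/100 = 20.0% and 20/95 = 21.1%. Showing both avoids silently treating an unknown result as negative.
- Reconcile Sections 8, 11, 16 and 17 so that they name the same patients.

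The cost is a wording change, one CRF item and a few indeterminate inspections to report. No extra patients or procedures are needed, and clinical care is unaffected.

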**Research procedures:**

1. Document the number of subjects who did and did not have any missed stones as identified by SpyGlass.
2. Document the number of stones missed if there were any.
3. Document clinical management after finding a stone.(eg: balloon sweep, lithotripsy, stent placement, etc.)
4. Follow-up contact with the participant  $\approx$ 3 months after the ERCP procedure if he/she is enrolled and had undergone cholangioscopy with Spyglass to document any recurrent stones/procedures/interventions.
5. Medical history will be obtained either directly from the patient or from the patient medical records which may also include questions about prior problems with medications used for sedation or other unusual medication reactions.
6. De-identified ERCP, endoscopic, EUS and SpyGlass images and/or video recordings may be collected for review, analysis, presentations and publications.

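### Sections 11 and 16 conflict on follow-up and data use when a procedure is stopped after cholangioscopy has started, so the 3-month recurrence rate may come out too low

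*Combined protocol and SAP*

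**What the plan says.** - **Section 11, Research procedures, item 4** makes the contact at about 3 months "if he/she is enrolled and had undergone cholangioscopy with Spyglass to document any recurrent stones/procedures/interventions". It does not ask whether the procedure was finished.
- **Section 16, first sentence,** applies when a clinical reason prevents the procedures from going ahead: "Consented patients will be withdrawn from participation and their data will not be used if the standard of care procedures described in the protocol cannot". (The quote stops before the verb.) The examples are "inaccessibility of bile duct, early termination of procedure due to complications etc".
- **Section 16, second sentence:** "The 3 month follow-up phone call will not be made if the standards of care procedures are not completed and data not collected". Two conditions are joined by "and".
- **Section 11, Clinically indicated standard of care procedure/s,** places POC itself under the standard-of-care heading ("the cholangioscope (Spyglass) will be inserted through the channel of the endoscope and into the bile duct"), together with the treatment of any residual stone that follows it. Where "the physician decides not to perform the POC then the subject will be deemed as screen failure and will not be counted" towards the results, the rule concerns patients who had no POC.
- **Section 12, Endpoint Variables,** defines the follow-up endpoint as "Recurrent stones within 3 months after POC, and documentation of cholecystectomy as applicable". **Statistical Methods, item 3,** analyses it thus: "The proportion of subjects with recurrent stones will be estimated, along with the associated exact 95% binomial confidence interval". Neither states the denominator or how a missing 3-month contact is handled.
- **Section 17** says that risks arising from the standard-of-care procedures are recorded on the case report form so that they can be analysed.

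**The concern.** Because POC and the treatment after it both belong to the standard-of-care procedures, a patient can have POC and still meet the Section 16 trigger, for instance when a complication ends the session during or after cholangioscopy. Section 11 says to contact that patient. Section 16 says to withdraw the patient and leave the data unused.

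If Section 16 is followed, patients leave the recurrence analysis because of how the procedure went, not at random. Treatment after POC is meant to deal with residual stones, and Section 4 says missed stones can lead to recurrent symptoms, pancreatitis and cholangitis. A link between an unfinished procedure and later events is therefore plausible. Three things are at stake: the 3-month recurrence proportion, the later course of patients with a complicated procedure, and, through the data bar, possibly the primary missed-stone proportion.

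**Working it through.** **1. The rules set side by side**

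| Situation | Section 11 | Section 16 | Conflict? |
|---|---|---|---|
| Duct inaccessible, no POC | Item 4 requires no contact | Withdrawn, data unused | No |
| Physician decides against POC | Screen failure, not counted | Not needed | No |
| Stopped for a complication before POC | Item 4 requires no contact | Withdrawn, data unused | No |
| Stopped for a complication after POC started | Contact required | Can be read as withdrawn, data unused; call withheld if data also not collected | **Yes** |

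Only the last row is in dispute. The call sentence alone does not create the conflict: if the POC findings were recorded, its second condition fails and the call survives. The first sentence of Section 16 does create it, since it withdraws the patient and bars the data whatever was recorded. A call made to such a patient could not enter the analysis. Section 17 pulls the other way, because it wants procedural risks recorded for analysis.

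**2. The plan's own figures**

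Exact (Clopper-Pearson) 95% intervals for 10, 20 and 30 of 100 come out at 4.9% to 17.6%, 12.7% to 29.2% and 21.2% to 40.0%, as printed in Section 12. Enrolling 140 with about 30% screen failure leaves 140 × 0.70 = 98, in line with the target of 100 who undergo POC (Section 8). The point changes none of these figures.

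**3. Possible size of the effect**

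From the documents: 100 POC patients. Assumed, because the documents are silent: k of the 100 unfinished (2, 5 or 10), recurrence p in the others (5% or 10%), and a risk ratio RR for unfinished procedures (1, 2 or 4).

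- Rate in all POC patients = [(100 − k) × p + k × p × RR] / 100
- Expected rate with the k patients dropped = p
- Understatement = p × k × (RR − 1) / 100

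Example: p = 10%, k = 10, RR = 4 gives (90 × 10% + 10 × 40%) / 100 = 13.0%, against 10.0% when they are dropped, a difference of 3.0 points.

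| p | k | RR = 1 | RR = 2 | RR = 4 |
|---|---|---|---|---|
| 5% | 2 | 0 | 0.1 | 0.3 |
| 5% | 5 | 0 | 0.25 | 0.75 |
| 5% | 10 | 0 | 0.5 | 1.5 |
| 10% | 2 | 0 | 0.2 | 0.6 |
| 10% | 5 | 0 | 0.5 | 1.5 |
| 10% | 10 | 0 | 1.0 | 3.0 |

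(Understatement in percentage points.) The largest relative fall is 3.0/13.0, or equally 1.5/6.5, about 23%.

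**4. Bounds that need no risk ratio**

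Suppose 5 recurrences are seen among the patients who are called.

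| k not called | Dropped | All 100, none of the k recur | All 100, all of the k recur |
|---|---|---|---|
| 2 | 5/98 = 5.1% (1.7 to 11.5) | 5.0% (1.6 to 11.3) | 7.0% (2.9 to 13.9) |
| 5 | 5/95 = 5.3% (1.7 to 11.9) | 5.0% (1.6 to 11.3) | 10.0% (4.9 to 17.6) |
| 10 | 5/90 = 5.6% (1.8 to 12.5) | 5.0% (1.6 to 11.3) | 15.0% (8.6 to 23.5) |

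If none of the uncalled patients recur, dropping them slightly overstates the rate. The direction is therefore probable, not certain.

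**The case against.** The best defence is that the sections can largely be read together. Section 16 cancels the call only when the procedures are unfinished and the data are also missing. Its first example, an inaccessible duct, means no POC, so Section 11 would not call that patient either. Section 17 implies that something is recorded in complicated cases, so the second condition would often not be met. All this is right as far as the call sentence goes. A reader might infer that every POC patient with an unfinished procedure loses the call; the text does not say so. What the defence does not answer is the sentence before it, which withdraws the patient and bars the data with no such second condition.

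A second objection also has force. If a session is cut short before clearance, the stones left behind are known. They are neither recurrent nor missed, and a later procedure may simply complete the treatment. Pooling them without distinction could inflate the recurrence rate. This bears on how the patients are reported, and is no reason to lose them.

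Third, this is a descriptive secondary proportion with no hypothesis test, and the number of patients may be very small. That is fair, and it limits the weight of the point. A reader might also infer that the two hospitals would follow different patients. The plan describes a single-center study with one IRB and one responsible principal investigator, so nothing in it shows that they would.

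**Conclusion.** The conflict is real and narrow. It concerns patients whose procedure is stopped after POC has started. Section 11 keeps them in follow-up, Section 16 can be read to remove them and their data, and nothing else in the plan decides between the two. Following Section 16 may make the 3-month recurrence rate too low: by 0 to 3.0 percentage points under the assumed counts, base rates and risk ratios, and by nothing if unfinished procedures carry no extra risk. The effect on the primary proportion is possible but was not sized.

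Two stronger conclusions are not supported. One is that the rate is bound to be too low: higher risk after an unfinished procedure is a plausible inference that the documents neither state nor quantify. The other is a fall of about 40%. It can be constructed from 3 events in 5 unfinished cases and 4 in the other 95 (7/100 = 7.0% against 4/95 = 4.2%), but that needs a 60% risk against 4.2%, roughly 14-fold, for which the documents give no basis.

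The case for a single rule does not depend on the size. It should be corrected, as a point of moderate weight.

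**What to change.** Reconcile Section 16 with Section 11, item 4:

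1. Limit the Section 16 withdrawal and data bar to patients in whom POC was not started. Amend both sentences, since changing the call sentence alone would leave the data unusable.
2. Keep every patient in whom POC was started in the data, and make the 3-month call unless the patient withdraws consent.
3. In Section 12, state the denominator of the recurrence proportion as patients in whom POC was started. Report those with an unfinished procedure on their own line as well, and count stones known to be left in place separately from recurrent or missed stones.
4. Give the number withdrawn with reasons and, where the 3-month contact is missing, best-case and worst-case bounds of the kind shown above.

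The change affects follow-up and analysis only, not clinical care. It costs a sentence or two in Section 16, a short addition to Section 12, one extra reporting line, and a few calls to patients who have already consented to the study.
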